7.2 Immune-Related Adverse Events

Blockade of immune checkpoints is associated with immune mediated adverse events (irAEs) due to disruption of normal immune tolerance (43, 66, 79). These irAEs include but are not limited to autoimmune diarrhea, colitis, hepatitis, pneumonitis, encephalitis, nephritis, myositis, autoimmune endocrinopathies, myocarditis, and Stevens Johnson Syndrome/Toxic Epidermal Necrolysis. Occurrence of such events may call for interruption and/or discontinuation of study drug pending further evaluation and reporting to the Sponsor as AESIs. Most low-grade irAEs can be managed symptomatically. Persistent low grade or moderate toxicities may require treatment with corticosteroids or in refractory cases other immune suppressing agents such as mycophenolate or infliximab. High-grade immune-related toxicities in most cases require treatment with high-dose corticosteroids.

Temporary interruptions of study drugs may be required in the event of treatment-related, immune-related toxicity. General guidelines for specific toxicity regarding dosing and treatment are provided below. Unless otherwise specified Grade 1 immune-related toxicities may be monitored without administering specific interventions. Guideline principles may be adapted to local standard of care at the Investigator's discretion.

7.2.1 Diarrhea or Colitis

Diarrhea that develops in patients while receiving study drugs may reflect immune reactivity against normal colonic epithelium and careful monitoring for potential immune-related colitis should be instituted. Patients who develop signs or symptoms including abdominal pain, bloating, nausea, vomiting, diarrhea, or blood in the stools should be evaluated carefully for potential colitis.

- Grade 1 diarrhea - Closely monitor the diarrhea until resolution.
- Grade 2 diarrhea - Increase frequency of monitoring until resolution. For management of symptoms:
 - Loperamide/diphenoxylate.
 - Low-dose steroids if clinically indicated.
 - Consider management of prolonged Grade 2 event lasting more than 5 to 7 days or relapsed diarrhea as Grade 3 diarrhea (see below).
- Grade 3 diarrhea - Hold study treatment. Hospitalize patient promptly for further evaluation and management, including the following:
 - Bowel rest.
 - Supplemental IV fluids with close monitoring of fluid and electrolyte status.
 - Monitor frequency of bowel movements.
 - Consider imaging to rule out bowel obstruction or perforation.
 - Consideration of colonoscopy as appropriate.
 - Implementation of initial empiric immune suppression consisting of IV corticosteroids using methylprednisolone at a dosage of 2 mg/kg/day (or equivalent) divided twice daily. As tolerated, patients may be converted to oral corticosteroids (i.e., prednisone 2 mg/kg/day divided twice daily) and tapered as appropriate guided by the patients' clinical status.
 - Taper corticosteroids as clinically indicated.
 - For patients with severe colitis, or those who do not respond to corticosteroids, additional immune suppression with anti-TNF- α antibodies (i.e., infliximab) should be considered early in the course.
 - Consider restarting study treatment if:
 - It is determined there is no colitis and an alternative cause of diarrhea is found, and
 - Diarrhea resolves to \leq Grade 1 within 14 days.
- Grade 4 diarrhea - discontinue study treatment and treat as for Grade 3.

7.2.2 Hepatic Toxicity

7.2.2.1 Elevations in Transaminases

- Grade 1 elevations - No specific therapy required.
- Grade 2 elevations - For elevations in transaminases 3 to 5 × ULN, rule out viral and other etiologies. Consider imaging studies such as ultrasound or CT scan and liver biopsy to ascertain etiology of liver dysfunction. Consider starting oral prednisone 60 mg/day divided twice daily, and hold study treatment.
 - If improvement to ≤ Grade 1 does not occur within 48 hours consider IV steroids such as methylprednisolone at 2 mg/kg/day divided twice daily or oral steroids such as prednisone 60 to 120 mg per day, divided twice daily.
 - Monitor liver function tests at least twice weekly (or more frequently as clinically appropriate in the judgment of the Investigator) until transaminases have returned to Grade 1 or baseline.
 - Taper oral steroids as clinically indicated with improvement in liver function.
 - Resume study treatment at the next scheduled dose if no more than two doses were missed.
 - If improvement to ≤ Grade 1 does not occur within 14 days, discontinue study treatment.
- Grade 3 elevations - Hold study treatment.
 - For elevations in transaminases > 8 × ULN, permanently discontinue study treatment.
 - Begin immediate IV steroids; suggest methylprednisolone at a dosage of 2 mg/kg/day divided twice daily.
 - Consider additional immune suppression with mycophenolate for patients who do not respond to corticosteroid therapy within 3 to 5 days.
 - Monitor liver function tests at least twice weekly (or more frequently as clinically appropriate in the judgment of the Investigator) until transaminases have returned to Grade 1 or baseline.
 - For elevations in transaminases > 5 but ≤ 8 × ULN:
 - Begin immediate IV steroids; suggest methylprednisolone at a dosage of 2 mg/kg/day divided twice daily.
 - Consider additional immune suppression as above for patients who do not respond to corticosteroid therapy within 3 to 5 days.

- Monitor liver function tests at least twice weekly (or more frequently as clinically appropriate in the judgment of the Investigator) until transaminases have returned to Grade 1 or baseline.
- If the elevation does not improve to Grade 2 within 7 days and to Grade 1 within 14 days, discontinue study treatment.
- Resume study treatment administration if following conditions are met:
 - Laboratory elevations improved to \leq Grade 2 within 7 days and improve to \leq Grade 1 or baseline within 14 days.
 - Steroids have been tapered to \leq 10 mg per day of prednisone or equivalent.
 - On resuming study treatment, AST, ALT, and total and direct bilirubin laboratory test values will be evaluated at least once per week for 3 consecutive weeks.
- Permanently discontinue study treatment in the case of a second increase of AST or ALT to \geq Grade 3.
- Grade 4 elevation - Discontinue study treatment and treat as for Grade 3 elevation.

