4.2 Dose Limiting Toxicity (Tebotelimab Cohort)

For the purposes of safety management and defining DLTs, the combination of enoblituzumab + tebotelimab will be treated as one entity. If a DLT is considered related to study treatment, no distinction will be made as to which agent is the causative agent and administration of both agents will be stopped.

Dose limiting toxicities will be based on treatment-emergent drug-related AEs (or laboratory abnormalities) occurring through Cycle 2 Day 7.

Patients in the Tebotelimab Cohort who experience DLT will discontinue study treatment.

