4.2.2 Non-hematologic Dose Limiting Toxicity

- Any intolerable Grade 2 toxicity that results in dose interruption lasting more than 20 days, or requires drug withdrawal.
- Non-hematologic DLT is defined as any \geq Grade 3 non-hematologic event with the following exceptions:
 - Grade 3 electrolyte abnormality that lasts less than 72 hours, that is not otherwise associated with clinical complications, and responds to medical intervention
 - Grade 3 fever that lasts < 72 hours and is not associated with hemodynamic compromise
 - Grade 3 nausea or vomiting that lasts < 72 hours and responds to medical intervention
 - Grade 3 amylase and/or lipase elevation that is not associated with either clinical or radiographic evidence suggestive of pancreatitis.
 - Grade 3 gastrointestinal AEs of diarrhea, constipation, abdominal pain, cramping, dyspepsia or dysphagia that resolves to \leq Grade 1 within 14 days with medical therapy

- Grade 3 fatigue that lasts < 7 days
- Grade 3 infusion related reaction or cytokine release syndrome that lasts < 12 hours and responds to medical intervention.
- Grade 3 or 4 endocrinopathy that is adequately controlled with hormone supplementation
- Grade 3 skin toxicity that resolves to \leq Grade 2 within 14 days of initiation of corticosteroids
- Grade 3 inflammatory reaction (e.g., with associated pain, swelling) attributed to a local antitumor response (e.g., inflammatory reaction at sites of metastatic disease, lymph nodes, etc.) that resolves to \leq Grade 2 within 7 days.

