4.3.1 Dose Delays

Tebotelimab Cohort

Patients who experience a Grade 2 to 4 AE that is potentially dose-limiting should have study drug held pending assessment, management, and resolution of the AE. If the AE is assessed as unrelated to study drug or does not meet DLT criteria, therapy may be restarted at the previous dose and schedule, after appropriate recovery.

Retifanlimab and Tebotelimab Cohorts

A dose delay of up to 20 days is allowed for patients experiencing AEs. In the case of abnormal troponins or N-terminal pro b-type natriuretic peptide (NT-proBNP) values, study drug must be withheld and a thorough cardiac assessment performed promptly to diagnose myocarditis or other cardiovascular diseases; the patient may resume study drugs if myocarditis is not confirmed. Refer to [Section 7](#) for specific guidance on restarting study therapy for IRR and irAEs. A dose delay of up to 20 days may also be permitted for reasons other than AEs. All procedures at the missed dosing visit should be performed and treatment reinstated as if the delay had not occurred.

Patients with infusion delays > 20 days will discontinue the study drug, complete the End of Treatment visit, and then enter the Post-treatment Follow-up Period.

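### After a Grade 2 transaminase elevation, Protocol 7.2.2.1 allows restart after up to two missed doses (42 days) while 4.3.1 stops treatment after any delay over 20 days, and no text says which governs; the case is rare and the point minor

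*Protocol*

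**What the plan says.** Protocol 7.2.2.1, for Grade 2 elevations, advises considering oral prednisone and holding study treatment. It gives two limits on restart. One counts doses: "Resume study treatment at the next scheduled dose if no more than two doses were missed". The other counts recovery time: if improvement to Grade 1 or below "does not occur within 14 days, discontinue study treatment".

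Protocol 4.3.1 covers both cohorts. It allows a delay of up to 20 days for adverse events and refers the reader to Section 7 "for specific guidance on restarting study therapy for IRR and irAEs". It closes with "Patients with infusion delays > 20 days will discontinue the study drug".

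Two other places bear on which limit prevails. Section 7.2 describes its own content as guidance: "Guideline principles may be adapted to local standard of care". In the Tebotelimab Cohort, 4.2.2 lists as dose limiting "Any intolerable Grade 2 toxicity that results in dose interruption lasting more than 20 days", and 4.2 adds "Patients in the Tebotelimab Cohort who experience DLT will discontinue study treatment".

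Dosing is every 21 days ± 3 days (6.5.1; Appendix 1, footnote a). The SAP has no rule on delays.

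**The concern.** One section permits a restart that another forbids. A site working from the hepatic guidance could re-expose a patient after liver toxicity when the dose-delay section takes that patient off treatment. Another site, with the same patient, could discontinue.

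What is at stake is consistent handling after liver toxicity, drug exposure, and the summaries of adverse events leading to discontinuation or interruption (Protocol 14.7.1; SAP 6.8.1).

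**Working it through.** The plan states no figure for this point, so there is none to reproduce. The check is calendar arithmetic and a comparison of the texts.

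**Inputs.** Dosing interval 21 ± 3 days (6.5.1, Appendix 1). Delay limit 20 days (4.3.1). Restart after at most two missed doses, and recovery within 14 days (7.2.2.1).

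**Step 1: length of the delay.** Let day 0 be the last dose. The next dose is due on day 21 and its window ends on day 24. With m missed doses, restart at the next scheduled dose falls on day 21 × (m + 1), ± 3. Delay is that day minus 21 (counted from the due date) or minus 24 (counted from the window end).

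| Missed doses | Restart day | Delay from due date | Delay from window end |
|---|---|---|---|
| 1 | 42 (39–45) | 21 (18–24): 4 of 7 window days over 20 | 18 (15–21): 1 of 7 over 20 |
| 2 | 63 (60–66) | 42 (39–45): 7 of 7 over 20 | 39 (36–42): 7 of 7 over 20 |

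Two missed doses exceed the limit by 42 − 20 = 22 days from the due date (19 to 25 with the window). They exceed it on either count. One missed dose falls on either side of the limit, depending on the count and the window.

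**Step 2: can the two-dose case arise?** To miss the doses on days 21 and 42 through slow recovery alone, the elevation must persist for at least 21 days, or 18 at the shortest interval. Both exceed 14, so the recovery rule would already have stopped treatment. Trying every onset and recovery day, with recovery within 14 days, at 18-, 21- and 24-day intervals gives a maximum of one missed dose.

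Suppose the elevation is found on the due date. The latest permitted recovery is day 21 + 14 = 35, and the next scheduled dose is day 42. Restart on day 63 needs a further hold of 63 − 35 = 28 days (25 to 31), passing over the day-42 dose. A prolonged steroid taper could explain this. For Grade 2, 7.2.2.1 mentions prednisone at 60 to 120 mg per day with a taper left to clinical judgement, and sets no steroid dose that must be reached before restart.

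**Step 3: does any text set precedence?**
- The pointer in 4.3.1 sends the reader to Section 7 but states no exception. The stop sentence comes after it and is unqualified.
- Section 7.2 presents itself as adaptable guidance. That favours the 20-day stop but does not state it.
- The Grade 2 DLT criterion in 4.2.2 uses the same 20 days. It applies to one cohort, for events through Cycle 2 Day 7, and hepatic DLTs have their own section (4.2.3).

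The balance leans towards 20 days, but nothing decides it.

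**Step 4: how many patients?** The documents do not allow an estimate. Protocol 2.3.2.2 does not list AST or ALT increase among related events in at least 5% of patients on enoblituzumab + pembrolizumab (133) or enoblituzumab alone (179), or among the related events on enoblituzumab + retifanlimab (12). For tebotelimab, 2.3.4.2 reports AST increased in 6.7% and ALT increased in 5.7% of 210 Cohort Expansion patients. If the AST rate carried over (an assumption: any grade, mixed tumours, monotherapy), 0.067 × 30 ≈ 2 Tebotelimab Cohort patients would have an AST increase. The share that is Grade 2, and the share of those with a two-dose gap, are not given.

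**The case against.** The best defence is that the rules can be read together. The stop in 4.3.1 is mandatory and the two-dose condition is permissive guidance, so a site that obeys 4.3.1 breaches nothing. The instruction to resume at the next scheduled dose, with the 14-day rule, makes a two-dose gap close to unreachable. On this view only loose wording remains.

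Much of this stands. It is why the point is minor, and why the two-dose case is called rare. It does not remove the problem. On the 20-day reading the two-dose allowance can never operate, yet it is printed as a restart rule. A site may also reasonably take the reference to Section 7 to mean that the specific rule governs. The 14-day rule limits recovery time, not the length of the hold after recovery.

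Two stronger readings are tempting and are not supported:
- A reader might infer that a single missed dose already breaks the 20-day limit. That is true nominally from the due date (21 days) but not from the window end (18 days), and 4.3.1 does not say which count applies.
- A reader might infer that the DLT criterion in 4.2.2 settles the matter at 20 days. Its scope is too narrow for that, as Step 3 shows.

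**Conclusion.** The inconsistency is real and narrow. For a two-dose gap after a Grade 2 transaminase elevation, 7.2.2.1 permits restart at 42 days (39 to 45) and 4.3.1 requires discontinuation beyond 20, with no stated precedence. Reaching that gap needs a hold beyond recovery, so the number of patients may be zero. The single-dose case is an ambiguity in how delay is counted, not a firm contradiction.

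This rests on reading a dose as one three-weekly administration of study treatment, and on restart at a scheduled visit within the ± 3-day window.

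A reader might also infer a threat to the primary result. The documents do not support that: neither the ORR definition nor the sample-size calculation (14 of 50 responses, 19% against 36%) uses a delay limit, so ORR, sample size and power are unaffected. Severity is minor.

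**What to change.** Make the two rules agree. The choice of limit belongs to the sponsor's medical team.

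(a) If 20 days is intended, replace the two-dose allowance in 7.2.2.1 with:

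> Resume study treatment at the next dosing visit after improvement to Grade 1 or below within 14 days, with steroids tapered as clinically indicated, provided the delay does not exceed the Section 4.3.1 limit.

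State in 4.3.1 the date from which delay is counted. If it is the due date, a nominal single missed dose (21 days) is one day over, so say that the held dose may be given at an adjusted visit by day 20. That fits the existing instruction in 4.3.1 that missed-visit procedures be performed and "treatment reinstated as if the delay had not occurred". Keep the anchor to a dosing visit: permitting restart simply on improvement could prompt early re-dosing while the patient is still on high-dose prednisone.

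(b) If a longer hold is intended, add to the 4.3.1 stop sentence:

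> except where Section 7.2 specifies a different limit

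Then say how this applies beside the Grade 2 DLT criterion of more than 20 days in 4.2.2.

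The cost is a protocol amendment or clarification letter with medical sign-off. There is no analysis, sample-size or enrolment cost.

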 - b. Absolute neutrophil count $\geq 1.5 \times 10^3/\mu\text{L}$ in the absence of any growth factor support within 28 days prior to the initiation of study drug.
 - c. ALT/AST $\leq 2.5 \times \text{ULN}$; for patients with hepatic metastases, ALT and AST $\leq 5 \times \text{ULN}$.
 - d. Total bilirubin $< 1.5 \times \text{ULN}$, except patients with Gilbert's syndrome, who may enroll if the conjugated bilirubin is within normal limits.
 - e. Creatinine $< 2 \text{ mg/dL}$, or a calculated or measured creatinine clearance $> 50 \text{ mL/min}$.
 - f. Negative serum pregnancy test, if applicable.
14. Women patients of child-bearing potential (WOCBP), defined as not surgically sterilized (hysterectomy, bilateral salpingectomy, and bilateral oophorectomy) and between menarche and 1-year post menopause, must have a negative serum pregnancy test performed within 72 hours prior to the initiation of study drug administration. Female patients must agree to abstain from egg donation during the course of the study.
15. WOCBP and male patients with partners of WOCBP must agree to use highly effective methods of contraception according to [Section 8.1.3](#) from the time of consent through 120 days after discontinuation of study drug administration. Male patients must agree to abstain from sperm donation during the course of the study.
16. WOCBP is not pregnant or breastfeeding or male patient is not expecting to father children within the projected duration of the study, starting with screening visit through 120 days after the last dose of study drug.

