7.2.2.2 Elevations in Total Bilirubin

- Grade 1 elevations - No specific therapy required.
- Grade 2 elevations - Hold study treatment until improvement to \leq Grade 1.
 - Rule out viral and other etiologies. Consider imaging studies such as ultrasound or CT scan and liver biopsy to ascertain etiology of liver dysfunction. Consider oral steroids.
 - If improvement to \leq Grade 1 does not occur within 14 days, discontinue study treatment and begin oral steroids.
- Grade 3 elevations - Hold study treatment.
 - For elevations in total bilirubin $> 5 \times$ ULN, permanently discontinue study treatment and initiate IV steroids, suggest methylprednisolone at a dosage of 2 mg/kg/day divided twice daily, and,
 - If no response to corticosteroid therapy within 3 to 5 days is observed, consider adding immune suppression therapy with mycophenolate.
 - Monitor liver function testing at least twice weekly (or more frequently as clinically appropriate in the judgment of the Investigator) until total bilirubin has returned to Grade 1 or baseline.
 - For elevations in total bilirubin > 3.0 but $\leq 5 \times$ ULN:

- Begin immediate IV steroids, suggest methylprednisolone at a dosage of 2 mg/kg/day divided twice daily. Consider additional immune suppression as above for patients who do not respond to corticosteroid therapy within 3 to 5 days.
- Monitor liver function including total bilirubin testing at least twice weekly (or more frequently as clinically appropriate in the judgment of the Investigator) until total bilirubin has returned to Grade 1 or baseline.
- If the elevation does not improve to Grade 2 within 7 days and to Grade 1 within 14 days, discontinue study treatment.
- Resume study treatment administration if:
 - Laboratory elevations downgrade to \leq Grade 2 within 7 days and improve to \leq Grade 1 or baseline within 14 days.
 - Steroids have been tapered to \leq 10 mg per day of prednisone or equivalent
 - On resuming study treatment, AST, ALT, and total bilirubin laboratory test values will be evaluated at least once per week for 3 consecutive weeks.
- Permanently discontinue study treatment in the case of a second increase of total bilirubin to \geq Grade 3.
- Grade 4 elevations - Discontinue study treatment and treat as for Grade 3 elevation.

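### Grade 3 hepatic rules (Protocol 7.2.2.1, and in wording 7.2.2.2): the stop line omits the baseline alternative that the resume line allows, so a patient back at a Grade 2 baseline meets both

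*Protocol*

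**What the plan says.** **Transaminases (Protocol 7.2.2.1).** Grade 3 is split at 8 × ULN. Above that, the instruction is to "permanently discontinue study treatment". From above 5 to 8 × ULN, treatment is held, IV steroids are started, and liver tests continue "until transaminases have returned to Grade 1 or baseline". Two lines then decide what happens next:

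- Stop: "If the elevation does not improve to Grade 2 within 7 days and to Grade 1 within 14 days, discontinue study treatment".
- Resume: Grade 2 or lower by day 7, then a day-14 target that allows "Grade 1 or baseline within 14 days", plus a steroid condition ("Steroids have been tapered to" at most 10 mg/day of prednisone equivalent).

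**Bilirubin (Protocol 7.2.2.2).** The tier above 3 and up to 5 × ULN repeats the same pair. Above 5 × ULN the instruction is to "permanently discontinue study treatment and initiate IV steroids".

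**Who can have a raised baseline.** Inclusion criterion 13c caps ALT/AST at 2.5 × ULN, but "for patients with hepatic metastases, ALT and AST" may be as high as 5 × ULN. Section 7.2.2.1 describes Grade 2 transaminases as 3 to 5 × ULN. Criterion 13d requires bilirubin below 1.5 × ULN except in Gilbert's syndrome, "who may enroll if the conjugated bilirubin is within normal limits".

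**Related text.** The hepatic DLT definition in 4.2.3 has an explicit rule for patients with Grade 1 or 2 transaminases at baseline. It also uses the baseline alternative in its own day-14 test, for transaminases and for bilirubin. Section 4.3.1 ends treatment after a delay of more than 20 days and sends sites to Section 7 for restart guidance. The preface to 7.2 describes its rules as guidance that the Investigator may adapt.

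**The concern.** The day-7 test is the same in both lines; the day-14 test is not. For a patient whose baseline is Grade 1 or normal this makes no difference. For a patient who entered at Grade 2, full recovery to the starting value satisfies the resume line and fails the stop line at the same time. One line keeps a recovered first-line patient on therapy and the other ends therapy for good.

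The study plans about 35 centers, so sites could decide the same case differently. The planned output most directly touched is the descriptive table of AEs that led to discontinuation (Protocol 14.7.1, SAP 6.8.1). The ORR definition, the sample size and the error rates are unaffected.

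**Working it through.** The plan has no figure to reproduce here. The check is logical: write both lines as conditions and run example courses through them.

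**Inputs.** Grade 2 ALT/AST = 3 to 5 × ULN and Grade 3 above 5 (7.2.2.1); baseline up to 5 × ULN with liver metastases (13c); steroid limit 10 mg/day (7.2.2.1); delay limit 20 days (4.3.1).

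**Rules.**

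- Stop = NOT (Grade ≤ 2 by day 7 AND Grade ≤ 1 by day 14).
- Resume = Grade ≤ 2 by day 7 AND (Grade ≤ 1 OR value ≤ baseline by day 14) AND steroids tapered.

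**Transaminase courses** (multiples of ULN, peak above 5 and at most 8):

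| Baseline | Day 7 | Day 14 | Steroids tapered | Stop | Resume |
|---|---|---|---|---|---|
| 1 | 4 | 1 | yes | no | yes |
| 2.5 | 4 | 2.5 | yes | no | yes |
| 4 | 4.5 | 2.9 | yes | no | yes |
| **4** | **4.5** | **4** | **yes** | **yes** | **yes** |
| **5** | **5** | **5** | **yes** | **yes** | **yes** |
| 4 | 4.5 | 4.5 | yes | yes | no |
| 4 | 6 | 4 | yes | yes | no |
| 4 | 4.5 | 4 | no | yes | no |

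The conflict appears only in the two bold rows: Grade 2 baseline, on time at day 7, back to baseline but not to Grade 1 by day 14, steroids tapered. A peak of 8.5 removes it (permanent stop), and so does a delay of 21 days (4.3.1).

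**Does the 20-day limit make the case moot?** No. If the rise is found on the dosing day, day 14 leaves 20 − 14 = 6 days. If it is found on a sample taken 3 days earlier, as Appendix 1 allows, day 14 leaves 20 − (14 − 3) = 9 days.

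**Bilirubin.** The lower edge of Grade 2 is not in the documents, so it is assumed to be 1.5, 2.0 or 2.4 × ULN. With peak 4, a baseline of 2.5 or 3.0 and timely return to it, both lines are met at each assumed edge. With baseline 1.4 (edge 1.5), only resume is met. With baseline 3.1 the day-7 target is missed, so resume is not met and there is no conflict.

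**Tebotelimab Cohort, DLT window.** Under 4.2.3, a Grade 3 transaminase rise in this tier that reaches Grade 2 by day 7 and baseline by day 14, with any steroids tapered by Day 14, is not a DLT. Section 4.3.1 then allows restart after appropriate recovery. Section 4.2 ends that window at Cycle 2 Day 7, and the Retifanlimab Cohort has no counterpart.

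**Effect on the table.** Each patient classified one way rather than the other moves the discontinuation percentage by 1/50 = 2.0 points (Retifanlimab) or 1/30 = 3.3 points (Tebotelimab).

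**After the edit.** With the baseline alternative added, Stop becomes NOT (Grade ≤ 2 by day 7 AND (Grade ≤ 1 OR value ≤ baseline by day 14)). This is the exact complement of the laboratory part of Resume, and the bold rows give resume only. One gap remains. A value of 4 × ULN on day 14 lies in the Grade 2 range, and the Grade 2 tier has its own 14-day stop line that requires Grade 1 with no baseline alternative. The edit therefore also needs a sentence on which tier governs.

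**The case against.** **An elevation could mean a rise over baseline.** Read by absolute multiples, a 13c patient at 4 × ULN would sit in the Grade 2 tier before the first dose and would have to stop within 14 days, which cannot be intended. If an elevation means a rise over the patient's own baseline, return to baseline ends it and the stop line is never triggered. This is the best argument on the other side, and it shows that the Grade 2 tier must be dealt with in the fix. It does not remove the conflict: the stop line names Grade 1 as its target, and 4.2.3 speaks of Grade 1 or 2 values at baseline, so grades there are not relative to baseline.

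**Stop only if both targets are missed.** Under that parse the recovered patient does not meet the stop line. But a patient with baseline 1 who is at 4 × ULN on days 7 and 14 would then meet neither line, and the parse departs from the parallel wording of 4.2.3.

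**Section 7.2 is adaptable guidance.** True. Steroids for immune-related events also involve the Medical Monitor (8.1.1), and AE-related discontinuations are reported within 24 hours (12.2.4.4). This lowers the severity, but it sets no precedence between the two lines.

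**Section 4.3.1 already permits restart.** This stands for the Tebotelimab Cohort through Cycle 2 Day 7, and the point is limited accordingly. The text is permissive and does not reach the other cohort or later cycles.

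**Conclusion.** The transaminase stop and resume lines contradict each other for a narrow, admissible group: liver-metastasis patients with baseline ALT/AST above 3 and up to 5 × ULN who recover to baseline on time, with steroids tapered and within the delay limit. The monitoring line, the resume line and 4.2.3 all carry the baseline alternative, so the stop line looks like an omission. Severity is minor.

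Three stronger readings are tempting and are not supported:

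- *The bilirubin rule is equally shown to fail.* The wording mismatch is there, but a real conflict needs a Gilbert's patient with a Grade 2 baseline, and the documents do not give the lower edge of that grade.
- *Both cohorts are exposed throughout.* Sections 4.3.1 and 4.2.3 already permit restart in the Tebotelimab DLT window.
- *The effect on the discontinuation table can be estimated.* The documents give no prevalence for the raised baselines, so only the per-patient shift of 2.0 or 3.3 points can be stated. As an unsourced illustration, 0 to 2 patients per cohort would mean 0 to 4.0 points (2/50) and 0 to 6.7 points (2/30).

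No efficacy analysis, sample size or error rate changes.

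**What to change.** In the Grade 3 stop lines of 7.2.2.1 and 7.2.2.2, add *or baseline* after *Grade 1*, matching the resume lines and 4.2.3. Add one sentence saying that a Grade 3 event that has returned to a Grade 2 baseline is governed by the Grade 3 resume conditions, not by the 14-day stop line of the Grade 2 tier. The wording of the Grade 2 tiers and criterion 13d can stay as they are.

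The cost is two words in two lines and one sentence, in the next amendment or a clarification to sites. No test, visit or analysis is added.
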